The image consists of a series of horizontal black bars of varying lengths and positions, set against a white background. The bars are irregular in length and position, creating a sense of a digital or abstract representation of data. Some bars have white segments or are partially cut off at the ends. The pattern is irregular and suggests a digital or abstract representation of data.

A series of 15 horizontal black bars of varying lengths, starting with a short bar and increasing to a long bar, then decreasing again. The bars are arranged vertically, with the first bar being the shortest and the last bar being the longest. The bars are separated by small gaps.

A large black rectangular redaction box covers the majority of the page content, from approximately y=113 to y=886. The redaction is composed of several horizontal black bars of varying lengths, with a few white spaces and small black marks visible within the redacted area.

## 6.3. Safety Analyses

Safety analyses will be performed on the Safety Analysis Set.

Safety parameters will be analyzed descriptively (see [Section 4.4.2](#) and [Section 4.4.3](#)) by treatment group and overall. No formal testing will be performed to compare the treatment groups.

### 6.3.1. Adverse Events

All AEs and changes in attributes (worsening and improvement) of AEs are reported in the database. An identification number serves to link the records considered by the investigator as describing the evolution of one and the same event.

#### 6.3.1.1. Definition of Treatment-Emergent Adverse Events

The analysis of AEs will be based on treatment-emergent events (TEAE). TEAEs are defined as

- Any AE with an onset date on or after the IP start date and no later than 14 days after last dose of IP, or any worsening of any AE on or after the IP start date.
- Improvement or no change of any ongoing AEs on or after the IP start date are not considered treatment-emergent. If an AE is ongoing at the time of first IP intake, if there is no change or an improvement in its toxicity grade or its seriousness status (reported in the 'Change in Adverse event details Entry' CRF page), this AE will not be considered as treatment-emergent.

#### 6.3.1.2. Coding of Reported Terms

All AE terms will be coded in the database using the latest version of MedDRA coding dictionary. AEs will be graded using the National Cancer Institute Common Terminology Criteria for Adverse Events (NCI CTCAE).

All tables will show the AE preferred terms grouped into system organ class. Subject listings will also show the reported terms (verbatim). Any other coding levels will only be shown in a listing summarizing coding unless explicitly mentioned otherwise.

#### 6.3.1.3. Allocation of Adverse Events to Analysis Periods

All AEs will be placed into analysis periods considering their start date.

The general rule for allocation of AEs to analysis periods follows:

$$\text{Analysis period start date} \leq \text{AE start date} \leq \text{analysis period end date}$$

If the start date of an AE is missing or incomplete to a level preventing a clear allocation of the AE to one single analysis period and no flag indicating timing relative to study medication is available, a worst-case consideration (see below) will be done aiming to allocate the AE to one

single analysis period, if possible. When a worst-case consideration is needed, the end date of the AE, if and as available, should also be considered; if such AEs clearly end on a given point, this will exclude the possibility to allocate the AE to an analysis period after that point.

- An AE which according to the available information of its start date could belong to the screening as well as to the treatment analysis period will only be placed in the treatment period.
- An AE with a missing start date will be allocated to the treatment period unless the “Prior to First GLPG3970/Placebo Treatment= “Yes”.

#### **6.3.1.4. Treatment Relatedness**

Following the guideline ICH-E3 Structure and Content of Clinical Study Reports (Step 4 Version), the originally reported relatedness to study drug of an AE will be dichotomized as follows:

- *Not study drug related*: all non-missing weaker levels of relatedness than ‘possibly drug related’.
- *Study drug related*: ‘possibly drug related’ and all stronger levels of relatedness (this class also includes any missing drug relatedness, as a worst-case consideration).

Only this dichotomized relatedness will be used in tables and can apply to different study drugs when relatedness has been collected separately per study drug; relatedness as originally reported will only be listed.

#### **6.3.1.5. Worst-Case Selections**

When cross-tabulating AE preferred terms versus an AE attribute (like intensity), only the worst-case within each same preferred term, same subject and same analysis period will be considered, i.e. when the same subject has more than once the same AE preferred term reported in the same treatment group, the subject will be counted only once and will be shown under the worst outcome (like the worst intensity for that AE in the concerned treatment period).

The severity grade of events for which the investigator did not record severity will be categorized as “missing” for tabular summaries and data listings. The missing category will be presented last in summary presentation.

#### **6.3.1.6. Calculation of Relative Days and Duration**

For each newly reported event, and reported worsening or improvement of an existing event, the start day in the study (the day of the AE start date relative to the date of first study drug administration), the start day in the analysis period, and the duration (in days) will be calculated. In addition, the relative day and duration will be derived for the entire event; that is, the full evolution of the event, including the initial reporting and all subsequent worsening and/or improvement.

Relative days and durations will only be listed.

See [Section 4.3.1](#) for the calculation of relative days.

#### **6.3.1.7. Events of Special Interest**

Not applicable.

#### **6.3.1.8. Presentation of Results**

The analysis will focus on AEs reported during the treatment period. AEs reported during the screening period will only be listed.

All AEs tables will show the number of subjects with TEAEs.

AEs which are not treatment-emergent will only be listed.

A summary table will be provided, showing the number (percent) of subjects with at least one:

- TEAE,
- IP-related TEAE,
- Serious TEAE,
- TEAE leading to death,
- TEAEs by worst intensity (CTCAE toxicity grade),
- TEAE leading to study drug discontinuation.

The AE terms will be presented sorted in descending order of frequency, prioritizing the GLPG3970 treatment group and then for placebo, first by system organ class, then by preferred term, and then alphabetically.

Frequency tabulations, by system organ class and preferred term, of the number (percent) of subjects with a TEAE will be presented. Similar tables will be provided by worst intensity, and for IP-related TEAEs, grade 3-4-5 TEAEs, serious TEAEs and TEAEs leading to study drug discontinuation of IP.

All AE data will also be listed, including separate lists for SAEs, AEs leading to death, and AEs leading to study drug discontinuation. Listings will clearly indicate AEs to be treatment-emergent or not.

In addition, AEs related to SARS-CoV-2 will be listed separately.

#### **6.3.1.9. EudraCT Adverse Events Reporting**

For the purpose of EudraCT reporting, the following tabulations will be created:

Frequency tabulations, by system organ class and preferred term, of the number (percent) of subjects with non-serious TEAE will be presented. A similar table will be provided for all serious

TEAEs, as well as a table for non-serious TEAEs reported in at least 2 subjects in any treatment group.

### **6.3.2. Laboratory Safety**

#### **6.3.2.1. Available Data**

Laboratory tests scheduled are described in the CSP section 8.5.2.

The statistical analyses will only present results in Standard International (SI) standardized units. Other units will not be presented.

Only data provided by the central laboratory will be used in tables and figures. Results from local labs will be listed only.

#### **6.3.2.2. Derivation Rules**

##### **Derived Laboratory Tests**

Not applicable.

##### **Fasted and Non-Fasted Results**

Laboratory tests that are sensitive to the fasting status: glucose, triglycerides.

For these laboratory tests, only results from blood samples drawn in a fasted state will be included in the analysis. Results from blood samples taken in a non-fasted (not fasting and fasting not declared) state will be listed only and no toxicities or abnormalities will be calculated. Laboratory results for which the fasting status is missing will be considered as taken non-fasted.

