8.5.2. Clinical Laboratory Evaluations

The following clinical laboratory tests will be performed:

- **Hematology:** hematocrit, mean corpuscular volume (MCV), mean corpuscular hemoglobin (MCH), mean corpuscular hemoglobin concentration (MCHC), hemoglobin, red blood cell count, red blood cell distribution width, white blood cell count, white blood cell differential count (absolute and relative), platelets, and erythrocyte sedimentation rate (erythrocyte sedimentation rate at screening only).

– **Coagulation:**

INR (only when increase in LFTs, see Section 6.4), activated partial thromboplastin time, and prothrombin time.

– **Clinical chemistry:**

fasting glucose (at baseline [Visit 1], Day 15 [Visit 3], and Day 43 [Visit 5] and the ED visit, if applicable), glycosylated hemoglobin (HbA1c), fasting insulin (at baseline [Visit 1], Day 15 [Visit 3], and Day 43 [Visit 5] and the ED visit, if applicable), homeostatic model assessment of insulin resistance (HOMA IR) (at baseline [Visit 1], Day 15 [Visit 3], and Day 43 [Visit 5] and the ED visit, if applicable), urea, creatinine, creatinine clearance (ClCr), uric acid, sodium, potassium, calcium (total), reflex calcium (free/ionized; only if serum calcium total is elevated), chloride, phosphorus/phosphate, AST, ALT, GGT, total bilirubin, alkaline phosphatase (alkaline phosphatase bone fractions only if alkaline phosphatase is elevated), lactate dehydrogenase, creatine phosphokinase (CK), albumin, total proteins, triglycerides, total cholesterol, high density lipoprotein cholesterol, low density lipoprotein cholesterol, lipase, amylase, high sensitivity CRP, high sensitivity Troponin I and Troponin T (Troponin I on Day 1, later during the study only when troponin T is elevated).

Homeostatic model assessment of insulin resistance (HOMA-IR, see Definition of Terms) and HDL/LDL ratio will be derived from clinical chemistry parameters. An estimate of the creatinine clearance (ClCr) based on the serum creatinine level will be calculated by the central laboratory using the Cockcroft-Gault formula (see Definition of Terms).

– **Urinalysis:**

Dipstick: pH, glucose, proteins (qualitative), blood, leukocytes, ketones.

Microscopic examination of the sediment for cellular elements (cylinders, erythrocytes, leukocytes), if indicated (when the test strip was positive for blood and/or proteins).

Quantitative urine proteins, only when the test strip was positive for proteins.

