#### **6.3.2.3. Definition of Toxicity Grades**

Toxicity grades will only be derived for laboratory tests for which toxicity grades are available.

Toxicity grades will be determined as implemented in the attached table ([Appendix I](#)).

For elevations (H1 to H4), values under the threshold of H1 are reported as 'Grade 0'. For elevations (L1 to L4), values above the threshold of L1 are reported as 'Grade 0'.

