Glucose (fasting)	<LLN	<55 mg/dL; <3.0 mmol/L	<40 mg/dL; <2.2 mmol/L	<30 mg/dL; <1.7 mmol/L	>ULN	>125 mg/dL; ≥6.95 mmol/L	>250 mg/dL; ≥13.89 mmol/L	≥500 mg/dL; ≥27.75 mmol/L

Parameter	L1	L2	L3	L4	H1	H2	H3	H4
Glucose ( non-fasting )	<LLN	<55 mg/dL; <3.0 mmol/L	<40 mg/dL; <2.2 mmol/L	<30 mg/dL; <1.7 mmol/L	>ULN	>160 mg/dL; ≥8.89 mmol/ L	>250 mg/dL; ≥13.89 mmol/ L	≥500 mg/dL; ≥27.75 mmol/L
HbA1c	NA	NA	NA	NA	> 6.0 %	> 6.5 %	NA	NA
Fasting insulin	<2.6 μU/mL or 18.1 pmol/L	NA	NA	NA	>24.9 μU/m or 172.9 pmol/L	NA	NA	NA
Cholesterol	NA	NA	NA	NA	>ULN	>300 mg/dL; ≥7.75 mmol/L	>400 mg/dL ; >10.34 mmol/L	>500 mg/dL; ≥12.92 mmol/L
Low-density lipoprotein (LDL)	NA	NA	NA	NA	NA	≥160 mg/dL; ≥4.12 mmol/ L	≥190 mg/dL; ≥4.90 mmol/ L	NA
High-density lipoprotein (HDL)	NA	<40 mg/dL; <1 mmol/L	NA	NA	NA	NA	NA	NA
Triglycerides	NA	NA	NA	NA	>ULN	>300 mg/dL; ≥3.42 mmol/ L	>500 mg/dL; ≥5.7 mmol/ L	>1,000 mg/d L; ≥11.4 mmol/L
Calcium ( corrected for albumin )	<LLN	<8.0 mg/dL; <2.0 mmol/L	<7.0 mg/dL; <1.75 mmol/L	<6.0 mg/dL; <1.5 mmol/L	>ULN	>11.5 mg/dL ; >2.9 mmol/L	>12.5 mg/dL ; >3.1 mmol/L	>13.5 mg/dL ; >3.4 mmol/L

Parameter	L1	L2	L3	L4	H1	H2	H3	H4
Ionized calcium	<LLN	<1.0 mmol/L	<0.9 mmol/L	<0.8 mmol/L	>ULN	>1.5 mmol/L	>1.6 mmol/L	>1.8 mmol/L
Sodium	<LLN	<130 mEq/L; <130 mmol/L	<125 mEq/L; <125 mmol/L	<120 mEq/L; <120 mmol/L	>ULN	>150 mEq/L; >150 mmol/L	>155 mEq/L; >155 mmol/L	>160 mEq/L; >160 mmol/L
Chloride	<LLN	NA	NA	NA	>ULN	NA	NA	NA
Potassium	<LLN	NA	<3.0 mmol/L	<2.5 mmol/L	>ULN	>5.5 mmol/L	>6.0 mmol/L	>7.0 mmol/L
Phosphate	<LLN	<2.0 mg/dL; <0.65 mmol/L	<1.4 mg/dL; <0.45 mmol/L	<1.0 mg/dL; <0.32 mmol/L	>ULN	NA	NA	NA
Creatine phosphokinase (CPK)	NA	NA	NA	NA	> ULN	>2.5 x ULN	>5 x ULN	>10 x ULN
Uric acid	NA	NA	NA	NA	>ULN	≥10 mg/dL; ≥0.59 mmol/L	≥12 mg/dL; ≥0.71 mmol/L	≥15 mg/dL; ≥0.89 mmol/L
Albumin	<LLN	<30 g/L	<20 g/L	NA	NA	NA	NA	NA
eGFR (or Cr/Cl)	<LLN	<60 ml/min/ 1.73 m 	<30 ml/min/ 1.73 m 	<15 ml/min/ 1.73 m 	NA	NA	NA	NA
Blood urea nitrogen (BUN)	NA	NA	NA	NA	>ULN	>2.5 ULN	>5 ULN	>10 ULN
25-hydroxyvitamin D	< 20 ng/mL or < 50 nmol/mL	NA	NA		> 60 ng/mL or > 125 nmol/mL	NA	NA	NA

Parameter	L1	L2	L3	L4	H1	H2	H3	H4
PTH (0-20y)	<9 pg/mL or 1 pmol/L	NA	NA	NA	> 52 pg/mL or 5.5 pmol/L	NA	NA	NA
PTH (>20y)	<10 pg/mL or 1.1 pmol/L	NA	NA	NA	> 65 pg/mL or 6.9 pmol/L	NA	NA	NA
TRAP5b	<LLN	NA	NA	NA	>ULN	NA	NA	NA
P1NP	<LLN	NA	NA	NA	>ULN	NA	NA	NA
CTX Type I Collagen (20y - 51y), female	NA	NA	NA	NA	>574 pg/mL	NA	NA	NA

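### The SAP's fasted-sample rule omits insulin, so insulin from a non-fasted or fasting-undeclared sample is still graded against fasting limits

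*SAP*

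**What the plan says.** **Fasting rule (SAP 6.3.2.2).** The tests concerned are given as a closed list: "Laboratory tests that are sensitive to the fasting status: glucose, triglycerides". The consequence is tied to that list: "For these laboratory tests, only results from blood samples drawn in a fasted state will be included in the analysis". Non-fasted results for the two tests are listed, with no toxicity grade or abnormality derived. Unknown status counts as fed: "Laboratory results for which the fasting status is missing will be considered as taken non-fasted".

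**Insulin in the protocol (8.5.2).** The chemistry panel includes "fasting insulin (at baseline [Visit 1], Day 15 [Visit 3], and Day 43 [Visit 5] and the ED visit, if applicable". The Schedule of Activities puts fasted glucose, fasted insulin and HOMA-IR at those same visits, where subjects must have gone at least 8 hours without food.

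**Grading (SAP 6.3.2.3 and Appendix I, Table 2).** "Toxicity grades will be determined as implemented in the attached table". The only insulin row is labelled "Fasting insulin", with L1 at "<2.6 μU/mL or 18.1 pmol/L" and H1 at ">24.9 μU/m or 172.9 pmol/L". All higher grades are not applicable. Glucose has both a fasting and a non-fasting row.

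**Presentation (SAP 6.3.2.9).** The continuous values of the metabolic markers (fasted insulin, HOMA-IR, HbA1c) are sent to section 6.5. The shift tables and the treatment-emergent abnormality tables carry no such exception.

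**The concern.** The protocol treats glucose, insulin and HOMA-IR as one fasting group. The SAP rule keeps glucose from that group, adds triglycerides and leaves insulin out, without giving a reason. Two results from one blood sample are then handled differently: if the subject has eaten, or the fasting status was not recorded, glucose is withheld from grading and insulin is not. Insulin rises after a meal, so a fed value compared with a fasting limit can be reported as a treatment-emergent abnormality that only reflects breakfast. With planned arms of 20 and 10, a single such subject is visible in the table.

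**Working it through.** The plan states no figure on this point, so the check is mainly a tracing of the text, followed by simple counts.

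**1. One fed or undeclared sample, followed through the SAP**

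| Step | Glucose | Insulin |
|---|---|---|
| Within SAP 6.3.2 (tests of Protocol 8.5.2) | yes | yes |
| Named in the fasting rule, 6.3.2.2 | yes | no |
| Row in Appendix I | fasting and non-fasting | fasting only |
| Toxicity grade (6.3.2.3) | not derived | derived |
| L/N/H class (6.3.2.4, all laboratory-provided tests) | not derived | derived |
| Shift and treatment-emergent tables (6.3.2.9) | left out | included |

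The L/N/H class uses the laboratory's own indicator. The laboratory's reference range is not in the documents. That it is a fasting range is an assumption, reasonable because the test is ordered as fasting insulin.

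**2. The limits.** The paired units agree: 18.1/2.6 = 6.96 and 172.9/24.9 = 6.94 pmol/L per µU/mL. The H1 limit is therefore 24.9 µU/mL, despite the clipped unit in the table. Any fed value above 24.9 becomes H1.

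**3. Direction of the error.** SAP 6.3.2.7 takes the worst grade over all post-baseline records, including unscheduled visits. SAP 6.3.2.6 calls a grade treatment-emergent when it is higher than at baseline or changes direction.
- Fasted baseline grade 0, one fed post-baseline value above 24.9: reported as treatment-emergent H1, although it is an effect of the meal.
- Fed baseline above 24.9 (graded H1), true fasted H1 later: not higher than baseline, so not reported as treatment-emergent.

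**4. Size per subject.** With the planned arms, and every subject having post-baseline insulin data, one misgraded subject moves the percentage by 1/20 = 5 points on GLPG3970 or 1/10 = 10 points on placebo.

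**5. How often a sample could be affected.** Scheduled insulin values: 30 subjects × 3 visits = 90, of which 30 × 2 = 60 are post-baseline. The documents give no rate of non-fasted or undeclared samples, so a range is assumed, with independence between samples.

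| Assumed rate r | Expected affected, 90 × r | P(at least one of 60), 1 − (1 − r)^60 |
|---|---|---|
| 2% | 1.8 | 0.702 |
| 5% | 4.5 | 0.954 |
| 10% | 9.0 | 0.998 |
| 20% | 18.0 | 1.000 |

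These are chances that a sample falls under the wrong rule. The chance of a wrong grade is lower, because an undeclared sample may in fact be fasted and a fed value need not exceed 24.9.

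**The case against.** The best defence is that the design already deals with this. Insulin is scheduled only at visits that subjects must attend fasting, the early-discontinuation visit included, and the parameter is called fasting or fasted insulin throughout. One could read that name as excluding a sample known to be fed. The consequence is also slight: insulin stops at grade 1, whereas Appendix I reserves the term marked abnormality for grade 2 and above, and SAP 6.3 plans no formal comparison of safety data.

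The second part stands and sets the size of the point. The first part stands only in so far as fed samples should be uncommon. Fasted glucose is tied to the same visits, yet the SAP still wrote a rule for fed and undeclared glucose, so such samples are foreseen. A parameter's name does not tell a programmer what to do with a result whose fasting status is missing. The SAP does tell them, but for the two named tests only.

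A reader might also suppose that early-discontinuation visits are the main source of fed samples. The documents give no rate for any visit, and the fasting requirement there is the same.

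**Conclusion.** The point holds as a gap in a stated rule. SAP 6.3.2.2 omits insulin, so the SAP grades insulin from a fed or undeclared sample against limits meant for fasted samples, while withholding glucose from the same sample. The size is 5 or 10 percentage points per misgraded subject in a descriptive table of grade 1 abnormalities, assuming full planned arms. Insulin cannot become a marked abnormality, and the primary endpoint is not affected.

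A stronger reading is tempting: that HOMA-IR is kept after its own glucose value has been removed, and that fed insulin values enter the mean summaries. The documents do not support either. SAP 6.3.2.9 places the continuous analysis of insulin and HOMA-IR in section 6.5, which is not visible in the public copy and may contain its own fasting rule. HOMA-IR has no row in Appendix I, so it is not toxicity-graded, and its formula is not visible either. All that can be said is that the visible text does not state what happens to HOMA-IR when its glucose is excluded.

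**What to change.** Add insulin to the list of fasting-sensitive tests in SAP 6.3.2.2, so that non-fasted or undeclared insulin is listed but neither graded nor flagged. For HOMA-IR and the continuous summaries, confirm that section 6.5 applies the same fasted-sample rule and put a cross-reference to it in 6.3.2.2.

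The cost is one line and a cross-reference. No value is lost from the listings, but some insulin results that were truly fasted and merely undeclared will leave the graded tables, as already happens for glucose. Two consequences should be settled with the change:
- Insulin is first scheduled at Visit 1. Excluding a fed baseline sample will usually leave the baseline missing, and SAP 6.3.2.6 then counts any later grade 1 as treatment-emergent.
- SAP 6.3.2.7 ends by setting the worst-case grade to missing if any record is missing. It should say that an excluded sample is simply left out of the worst-case selection.

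### Glucose from a non-fasted or status-unknown sample is never graded, although Appendix I has a non-fasting row whose severe limits equal the fasting ones

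*SAP*

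**What the plan says.** SAP 6.3.2.2 names glucose and triglycerides as sensitive to fasting. For these tests "only results from blood samples drawn in a fasted state will be included in the analysis". Results from non-fasted samples "state will be listed only and no toxicities or abnormalities will be calculated". The same paragraph adds: "Laboratory results for which the fasting status is missing will be considered as taken non-fasted".

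SAP 6.3.2.3 then says: "Toxicity grades will be determined as implemented in the attached table". That table is Appendix I. Its blood chemistry part has two glucose rows, one fasting and one non-fasting, each graded in both directions.

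Four other places bear on the point:
- SAP 6.3.2.4 assigns a low, normal or high class to every test that the laboratory provides.
- SAP 6.3.2.7 derives worst-case grades from all post-baseline records that are not missing, including unscheduled and follow-up visits.
- SAP 6.3.2.9 names both glucose and fasted glucose among the tests to be summarised.
- The closing note of Appendix I calls any treatment-emergent grade 2 or higher a marked abnormality, to be described in the study report.

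**The concern.** Restricting glucose to fasted samples is sensible for means and changes over time, because food shifts the level. It is harder to defend for severe values. Food does not explain a low glucose, and the SAP's own grade 3 and 4 limits take no account of fasting. Under 6.3.2.2 such a value gets neither a grade nor a low/normal/high class, so it cannot enter the shift, worst-case or treatment-emergent tables, and it cannot trigger the marked-abnormality description.

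The treatment of missing status also runs against the rest of the safety section. Missing relatedness counts as related (6.3.1.4). An adverse event with no start date goes to the treatment period unless it is flagged as earlier (6.3.1.3). A missing baseline makes any later grade treatment-emergent (6.3.2.6). In each case missing information leads towards inclusion; a missing fasting flag leads to exclusion.

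The trial follows fasting glucose, insulin, HOMA-IR and HbA1c (protocol 8.5.2), so a gap in glucose grading matters more here than it would for an incidental test.

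**Working it through.** The plan states no figure on this point. The check compares the two Appendix I rows and then asks which samples the rule can reach.

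**Step 1: the two glucose rows.**

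| Grade | Fasting | Non-fasting | Same? |
|---|---|---|---|
| L1 | below LLN | below LLN | yes |
| L2 | <55 mg/dL (<3.0 mmol/L) | <55 mg/dL (<3.0 mmol/L) | yes |
| L3 | <40 mg/dL (<2.2 mmol/L) | <40 mg/dL (<2.2 mmol/L) | yes |
| L4 | "<30 mg/dL; <1.7 mmol/L" | "<30 mg/dL; <1.7 mmol/L" | yes |
| H1 | above ULN | above ULN | yes |
| H2 | ">125 mg/dL; ≥6.95 mmol/L" | ">160 mg/dL; ≥8.89 mmol/ L" | no |
| H3 | >250 mg/dL (≥13.89 mmol/L) | >250 mg/dL (≥13.89 mmol/L) | yes |
| H4 | "≥500 mg/dL; ≥27.75 mmol/L" | "≥500 mg/dL; ≥27.75 mmol/L" | yes |

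Unit check, assuming 18.016 mg/dL per mmol/L: 55, 40, 30, 125, 160, 250 and 500 mg/dL give 3.05, 2.22, 1.67, 6.94, 8.88, 13.88 and 27.75 mmol/L. These match the printed values to within about 0.05, so the two units do not conflict in any way that matters here.

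**Step 2: two examples.** A glucose of 1.6 mmol/L is below 1.7 and is L4 on either row. A glucose of 28 mmol/L is at or above 27.75 and is H4 on either row. If the sample is non-fasted or undeclared, 6.3.2.2 gives neither value a grade.

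**Step 3: where the rows disagree.** The only band is 6.95 to 8.89 mmol/L. A value of 7.5 mmol/L is H2 if fasted and at most H1 if not. Unknown fasting status therefore creates real doubt about the grade in this band only.

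**Step 4: which samples are affected.** Safety chemistry is drawn after baseline at Visits 3, 4, 5 (or early discontinuation) and follow-up. Protocol 8.5.2 and footnote 7 of the schedule plan glucose only as fasting glucose at Visits 1, 3, 5 and early discontinuation. That leaves three sources:
- subjects who came without fasting;
- samples with no fasting flag;
- unscheduled samples sent to the central laboratory.

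The documents do not say whether glucose is also reported at Visit 4 or follow-up, and they give no count for any source.

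**Step 5: weight of one case.** With planned arms of 20 and 10, one omitted subject is 1/20 = 5 percentage points on GLPG3970 or 1/10 = 10 on placebo, if every subject has post-baseline glucose data.

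**The case against.** The strongest reply has four parts.

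**The row may be a leftover.** Appendix I warns that it may hold tests not measured in this study. It grades a collagen marker for men over 71 in a trial of subjects under 65. An unused row is then no contradiction, and 6.3.2.2 governs as the specific rule. This stands as far as the row goes. It does not explain why severe values with identical limits should go ungraded.

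**Severe values are seen elsewhere.** The values are listed. Protocol 5.5 sets laboratory alerts at Grade 3 and above, and the internal committee reviews unblinded safety data. Clinically significant values become adverse events (protocol 8.5.2 and 11.1.5) and reach the treatment-emergent event tables, which include a grade 3 to 5 table (SAP 6.3.1.8). A reader might infer that such a value is missing from every toxicity table; that goes too far. The adverse-event route does, however, depend on the investigator's judgement, and protocol 11.2.3 allows its grade to differ from the laboratory grade.

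**Few samples are affected.** A reader might infer that half of the post-baseline visits yield ungraded glucose, since fasting is required at two of four, or that 6.3.2.9 shows non-fasted values are expected because it names glucose twice. Neither is supported. No glucose is scheduled at the other two visits, and the double naming may be loose wording.

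**Grading has a cost.** Post-meal values above the ULN, set against a fasted baseline, can produce treatment-emergent H1 shifts that reflect food. Putting undeclared samples on the non-fasting row would move a truly fasted 7.5 mmol/L from H2 to at most H1 and out of the marked category. Both points are right, and they shape the remedy.

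**Conclusion.** The point holds in a limited form. The SAP withholds every grade and abnormality class from glucose in non-fasted or undeclared samples, no other section restores them, and fasting status gives no reason to do so for L1 to L4, H3 or H4. The loss is confined to laboratory outputs based on grades or classes: toxicity, shift, worst-case, treatment-emergent and marked-abnormality.

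The number of samples is probably small. This rests on the schedule being followed and on few fasting flags being missing; the documents cannot confirm either. The primary analysis, the significance level and the sample size are untouched. This is a worthwhile, low-cost improvement to safety reporting and does not threaten the trial's conclusions.

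**What to change.** Amend SAP 6.3.2.2 as follows:
- Grade glucose from declared non-fasted samples on the Appendix I non-fasting row.
- For undeclared samples, apply at least the grades that do not depend on fasting: L1 to L4, H3 and H4.
- Flag fasting status on every graded glucose record, and include these records in the worst-case, shift, treatment-emergent and marked-abnormality outputs.
- Keep the fasted-only restriction for the continuous glucose summaries and for triglycerides.

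Bring 6.3.2.7 and 6.3.2.9 into line. In 6.3.2.7, choose the worst case by grade. The present wording ties it to the highest value, and with two rows a non-fasted value between 7.5 and 8.89 mmol/L would be at most H1 while a fasted 7.5 is H2. In 6.3.2.9, say whether glucose and fasted glucose are one test or two. State also whether the low/normal/high class of 6.3.2.4 applies to these samples.

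The cost is a few lines of SAP text and a small programming change, with no new data collection. The downside is some H1 or H2 grades caused by food. The fasting flag, or a separate presentation of the non-fasted grades, deals with that. Results from local laboratories stay in listings only under 6.3.2.1, so the change reaches central-laboratory samples alone.
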